# LIST OF ABBREVIATIONS

AE	Adverse Event		
AChE	Acetylcholine esterase		
ADA	American Dietetic Association		
ADL	Activities of Daily Living		
AE	Adverse Event		
ALT	Alanine Aminotransferase		
ALC	Absolute Lymphocyte Count		
ALP	Alkaline phosphatase		
AST	Aspartate Aminotransferase		
aPTT	Activated Partial Thrombonlastin Time		
ASCO	American Society of Clinical Oncology		
BUN	Blood Urea Nitrogen		
CBC	Complete Blood Count		
CMP	Comprehensive Metabolic Panel		
CP	Complete Desponse		
СТ	Computed Tomography		
CTCAE	Common Torminology Critorio for Advorse Events		
DIT	Dess Limiting Touisity		
DLI	Dose Limiting Toxicity		
DSMC	Data and Safety Monitoring Committee		
ECOG	Eastern Cooperative Oncology Group		
F ° I ′ 4	Free Thyroxine		
GI	Gastrointestinal		
H&PE	History & Physical Exam		
INR	International Normalized Ratio		
irAE	Immune- Related Adverse Event		
IRR	Infusion Related Reaction		
IDS	Infectious Disease Service		
ILD	Interstitial Lung Disease		
IM	Intramuscular		
IV	Intravenous		
IVIG	Intravenous Immunoglobulin		
KPS	Karnofsky Performance Status		
LFT	Liver Function Test		
LLN	Lower Limit of Normal MTD		
	Maximum Tolerated Dose		
MRI	Magnetic Resonance Imaging		
NCCN	National Comprehensive Cancer Network		
NCI	National Cancer Institute		
ORR	Overall Response Rate or Objective Response Rate		
OS.	Overall Survival		
PBMCs	Peripheral Blood Mononuclear Cells		
PCP	Pneumocystis Pneumonia		
PD	Progressive Disease		
PFS	Progression Free Survival		
PO(or n o)	Per os/by mouth/orally		
PR	Partial Response		
PT	Prothrombin time		
т т РТТ	Partial Thrombonlastin Time		
	Padiatharany		
	Radiomerapy		
RAINU	Cariana A drama Errort		
SAE	Serious Adverse Event		
SD	Stable Disease		
SGOT	Serum Glutamic Oxaloacetic Transaminase		
SPGT	Serum Glutamic Pyruvic Transaminase		

ТВ	Total Bilirubin
TMZ	Temozolomide
TNF	Tumor Necrosis factor
TFTs	Thyroid function tests
TSH	Thyroid Stimulating Hormone
ULN	Upper limit of normal
WBC	White Blood Cells

# STUDY SCHEMA

# STUDY SUMMARY

	A Phase II, open label, single center study of pre-surgical and adjuvant treatment of recurrent glioblastoma with Tremelimumab and MEDI4736 alone and in combination to
Title	determine immunologic changes from treatment.
Version	11.29.18
Study Design	Phase II trial
Study Center(s)	Robert H. Lurie Cancer Center of Northwestern University.
Objectives	
 
Primary: 
 
To determine the T-cell changes that occur in recurrent GBM treated with tremelimumab and durvalumab as single agents and in combination.
 
 
 
Secondary: 
 
To evaluate the safety of either tremelimumab or MEDI4736 alone and in combination in patients with recurrent GBM.
 
To determine post-surgery, the time to progression (per Modified RANO criteria and iRANO criteria, see below) for patients treated with either Tremelimumab or MEDI4736 alone and in combination of both.
 
To determine post-surgery, the overall survival for patients treated with Tremelimumab or MEDI4736 alone and in combination of both.
 
To assess post-surgery, the MRI changes in patients treated with either Tremelimumab or MEDI4736 alone and in combination of both.
 
 
 
Exploratory: 
 
To correlate T-cell changes and PDL1 expression with patient outcomes.
 
 
 

Sample Size	There will be three groups of patients, one group on each agent alone and one group treated with the combination agents. A total of 10 evaluable patients per group will be necessary for study endpoints. To attain 10 patients in each arm who are evaluable for the primary endpoint, a total of 45 patients will be accrued to the study. Sample sizes of 10 per group allow for the estimation of the proportion of responders in evaluable patients to be within 31% of its true value with 95% confidence. Mean change will be compared between arms. Using standard deviations of change, a sample size of 10 per group will allow the detection of differences of 1.25 standard deviations between groups with 80% power assuming a two-tailed test and a Type I error rate of 5%.

Key Eligibility Criteria	
 
Patients must nave a grade IV glioma that has failed standard RT and TMZ.
 
Patients must have had radiographic evidence of tumor progression by brain MRI or CT scan with contrast.
 
Patients must be > 12 weeks from completion of radiation therapy unless there is tissue confirmation of tumor recurrence or there is progression outside the radiation treatment field.
 
Prior therapy with gamma knife or other focal high-dose radiotherapy is allowed, but the patient must have subsequent histologic documentation of recurrence, unless the recurrence occurs remote from the treated site.
 
Patients must be surgical resection candidates.
 
Have resolved toxicity (>CTCAE grade < 2) from previous anti-cancer therapy.
 
Life expectancy of ≥ 12 weeks
 
Patients can only be on non-enzyme inducing anti-convulsants. If they are on an enzyme inducing anti-convulsant, they may be converted to a non-enzyme inducing anti-convulsants but they will need a 2 week wash out period from time of drug discontinuation.
 

Treatment Plan	
 
Patients will be randomly assigned to each arm using block randomization.
 
Treatment Arms:
 
Arm 1) Tremelimumab- 75 mg every 4 weeks. The 1st dose will be given 14 days pre-surgery. The drug will be restarted 14 days after surgery once the surgical wound has healed and then every 4 weeks after surgery. If there is no progression of disease, they will continue on treatment for up to 24 months.
 
Arm 2) MEDI4736- 750 mg every 2 weeks. The 1st dose will be given 14 days presurgery. The drug will be restarted 14 days after surgery once the surgical wound has healed and then every 2 weeks after surgery. If there is no progression of disease, they will continue on treatment for up to 24 months.
 
Arm 3) Tremelimumab 75 mg + MEDI4736 750mg. The 1st dose will be given 14 days pre-surgery. The drug will be restarted 14 days after surgery once the surgical wound has healed. Tremelimumab 75 mg + MEDI4736 750mg. The 1st dose will be given 14 days pre-surgery. The drug will be administered IV every 4 weeks (Day 1 of each cycle) and MEDI4736 750mg every 2 weeks (Day 1 and Day 15 of each cycle) until the patients have received 7 doses of Tremelimumab and 14 doses of MEDI4736. Thereafter, from Cycle 7 (Week 25), Tremelimumab will be given every 12 weeks (+/-7 days) and MEDI4736 will be given every 2 weeks (+/- 2 days) until permanent discontinuation criteria (e.g. disease progression) is met. If there is no progression of disease, they will continue on treatment for up to 24 months.
 

Statistical Methodology	Immunologic measures will be summarized over the three or more time points (pre- treatment, following first treatment/pre-surgery, and post-surgery) and changes in these measures will be assessed using repeated measures analysis of variance or Cochran's Q, followed by the paired t-test or the signed rank test for pairwise comparisons using Bonferroni corrections. Safety of the agents alone or in combination will be assessed by summarizing the frequency of adverse events by type, timing, grade and attribution. Immunologic changes will be correlated with MRIs in a descriptive fashion. The secondary endpoint of progression-free survival as well as overall survival will be analyzed using Kaplan-Meier curves. Immunologic changes of T-cells and PDL1 levels will be correlated to survival outcomes using Cox regression analysis. MRI changes will be summarized using means or proportions and statistically analyzed using the signed rank test.

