## 4.0 TREATMENT PLAN

## 4.1 Overview

Patients will be treated with either Tremelimumab 75 mg alone, MEDI4736 750 mg alone, or both in combination. Patients will be randomly allocated using block randomization to ensure equal sample sizes per arm. Up to 45 patients (15 per arm) will be randomized to ensure that 30 patients are evaluable for immunologic response (10 per arm).

Patients will then undergo a surgical resection of their tumor that is part of their medical care 2 weeks later to remove the tumor. Two weeks is expected to be enough time for immunologic changes to occur in the tumor. Standard pre-surgical testing will be done prior to surgery. At the time of surgery, tissue will be removed for local pathology review and send to [name] for evaluation (see Section 9.0 for details).

Post-operative care will be standard for patients who undergo a craniotomy and tumor resection at NMH. Patients will have a standard post-operative MRI or CT scan of the brain within 72 hours of surgery. Following surgery, patients will resume treatment on the same regimen they were assigned to receive before surgery. Treatment may continue until disease progression or unacceptable toxicity.

Treatment Administration Summary					
Arm	Treatment	Dose	Route	Schedule	Supportive Therapies**
1	Tremelimumab monotherapy	75 mg	IV at 250ml/hr	Once within 14 d (+/-3) pre-surgery. Adjuvant: Every 4 weeks	Acetaminophen and/or antihistamine or equivalent 
2	MEDI4736 monotherapy	750 mg	IV over 60min+/-5 mins 	Once within 14 d (+/-3) pre-surgery. Adjuvant: Every 2 weeks	Acetaminophen and/or antihistamine or equivalent 

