#### 4.5 **Duration of Therapy**

Patients on all arms will remain on study as long as there is no disease progression for up to 24 months or until any of the following occur:

- Disease progression
- Development of an inter-current illness that prevents further administration of treatment
- Unacceptable adverse event(s)
  - See section on dose modifications: Treatment delay of > 4 weeks due to treatment related toxicities.
  - Protracted (>2 weeks) medically concerning grade 2 cardiac, pulmonary, renal, gastrointestinal, skin, or CNS toxicities.
- The treating investigator determines that the patient should be taken off treatment for any reason (i.e. changes in condition, inability to comply with study treatment or procedures).

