#### 4.6 Duration of Follow Up

All subjects will be followed for survival for up to 2 years/24 months from stopping study treatment. Subjects who decline to return to the site for evaluations will be offered follow-up by phone every 8-16 weeks as an alternative.

Note that patients who discontinue treatment permanently for any reason other than progression will be followed for evidence of tumor response and disease status.

Any patient who withdraws their consent, will be considered as an early discontinuation, and may be replaced if this occurs before they have received the first dose of treatment. Patients who withdraw consent but receive at least one dose of treatment will be evaluable for toxicity even if they are not fully evaluable for response. The accrual goal has been set to allow up to 45 patients to be enrolled in order to allow for early discontinuations.

If a patient withdraws consent, no further treatment or study-specific testing will be completed. The primary reason for a patient's withdrawal from the study is to be recorded in the source documents. All patients will be followed until death or 2 years/24 months from stopping treatment.

Subjects who are permanently discontinued from further receipt of investigational product, regardless of the reason (withdrawal of consent, due to an AE, other), will be identified as having permanently discontinued treatment.

Subjects who are permanently discontinued from receiving investigational product will be followed for safety for 30 days post last-dose visit including the collection of any protocol-specified blood specimens, unless consent is withdrawn or the subject is lost to follow-up or enrolled in another clinical study. If a subject is enrolled in another clinical study, they will be followed until all AEs are resolved or stable. If enrolled onto another clinical study, it is not necessary to follow the subject for survival or progression.

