-  During adjuvant treatment, one cycle is defined as 4 weeks for patients on Arms 1 and 2. For patients on Arm 3, please refer to the schedule outlined in footnote #14.
-  Blood samples will be collected for various research tests at 1 st pre-operative treatment, day of surgery, C1D1 and at each adjuvant treatment imaging visits (i.e. every 2 cycles or 8 weeks):
  - a) 10ml blood in one 10ml Sodium heparin tube: To be collected and processed by the [name] lab for peripheral blood lymphocytes (PBLs).
  - b) 8m (2x4ml) blood in two 5ml EDTA (purple top) tubes: To be collected and processed by the [name] lab for gene expression profile using mononuclear cells.
  - c) 10ml blood in one 10ml red top tube: To be collected and processed by the [name] lab for analysis of tryptophan catabolites and cytokines.
  - Please refer to section 9.0 and laboratory manual for more details
-  Any patient who undergoes further surgery will have the option to use their tumor tissue for research to understand the immunologic changes occurring at the time of presumed drug failure. Please refer to Section 9 and laboratory manual for details.
-  Follow up for disease progression (if not already documented) and survival will occur every 8-16 weeks once off treatment. All patients will be followed until death or 2 years/24 months from stopping treatment.
-  Patients enrolled on Arm 1 will receive tremelimumab monotherapy: one 75 mg dose IV on day 1 (+/- 2 days) per cycle (every 4 weeks) up to 24 months.
-  Patients enrolled on Arm 2 will receive MEDI4736 monotherapy: one 750 mg dose IV on days 1 and 15 (+/- 2 days allowed for each) per cycle (every 2 weeks) up to 24 months.
-  Patients enrolled on Arm 3 will receive combination therapy (tremelimumab 75 mg + MEDI4736 750 mg) according to the following schedule: Tremelimumab will be administered IV every 4 weeks (Day 1 of each cycle) and MEDI4736 750mg every 2 weeks (Day 1 and Day 15 of each cycle) until the patients have received 7 doses of Tremelimumab and 14 doses of MEDI4736. Thereafter, from Cycle 7 (Week 25), Tremelimumab will be given every 12 weeks (+/-7 days) and MEDI4736 will be given every 2 weeks (+/- 2 days) until permanent discontinuation criteria (e.g. disease progression) is met. If there is no progression of disease, they will continue on treatment for up to 24 months.

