# 6.4 Response Assessment (Modified RANO criteria)

The response to immunotherapy may differ from the typical responses observed with cytotoxic chemotherapy including the following (Wolchok et al 2009, Nishino et al 2013):

- Response to immunotherapy may be delayed
- Response to immunotherapy may occur after PD by conventional criteria
- The appearance of new lesions may not represent PD with immunotherapy
- SD while on immunotherapy may be durable and represent clinical benefit

Based on the above-described unique response to immunotherapy and based on guidelines from regulatory agencies, e.g., European Medicines Agency's "Guideline on the evaluation of anticancer medicinal products in man" (EMA/CHMP/205/95/Rev.4) for immune modulating anticancer compounds, the study use a modified RANO criteria to define PD:

Progressive disease post-baseline is defined as one or more of the following:

- New contrast-enhancing lesion outside of radiation field on decreasing, stable, or increasing doses of corticosteroids.
- Increase by > 50% (modified from >25% according to published RANO criteria) enhancement from the first post-surgical scan, or a subsequent scan with smaller tumor size, and the scan 8 weeks or later on stable or increasing doses of corticosteroids.
- Clinical deterioration not attributable to concurrent medication or comorbid conditions is sufficient to declare progression on current treatment.

Treatment with MEDI4736, Tremelimumab or both would continue between the initial assessment of progression and confirmation for progression. In addition, subjects may continue to receive MEDI4736, Tremelimumab or both beyond confirmed PD in the absence of clinically significant deterioration and if investigators consider that subjects continue to receive benefit from treatment.

As a secondary measure, for all response assessments, iRANO will be used for assessment.

RANO and iRANO criteria (iRANO= immunotherapy Response Assessment in Neuro-Oncology)						
	Response	Malignant glioma	Low-grade glioma	Brain metastasis		

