**Time to Progression:** From date of first treatment to the date of first observation of definitive progressive disease, non-reversible neurologic progression or increasing steroid requirements (applies to stable disease only), death due to any cause, or early discontinuation of treatment. Patients not reaching the progression endpoint at last follow-up will be censored at that time.

**Time to Death**: From date of first treatment to date of death due to any cause. Patients alive at last follow-up will be censored at that time.

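### Survival follow-up is timed from stopping treatment and waived on entry to another study, so censoring in the overall survival curve may depend on prognosis

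*Combined protocol and SAP*

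**What the plan says.** **Time origin and censoring.** Section 10.3 defines time to death as "From date of first treatment to date of death due to any cause" and adds "Patients alive at last follow-up will be censored at that time". The planned method, in the Study Summary and again in 10.3, is Kaplan-Meier: "The secondary endpoint of progression-free survival as well as overall survival will be analyzed using Kaplan-Meier curves". No landmark, data cut-off or allowance for dependent censoring is given.

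**End of follow-up.** Section 4.6 states "All subjects will be followed for survival for up to 2 years/24 months from stopping study treatment". Footnote 11 of the Section 5.2 schedule has the same rule: "All patients will be followed until death or 2 years/24 months from stopping treatment".

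**Time on treatment.** Section 4.5 states "Patients on all arms will remain on study as long as there is no disease progression for up to 24 months" and then lists other reasons for stopping, including intercurrent illness and unacceptable adverse events. Section 4.1 states "Treatment may continue until disease progression or unacceptable toxicity". Section 6.4 is looser: "subjects may continue to receive MEDI4736, Tremelimumab or both beyond confirmed PD in the absence of clinically significant deterioration", provided the investigator sees continuing benefit.

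**Exception.** The last paragraph of Section 4.6 says survival and progression need not be tracked once a patient has joined a different trial. This does not fit the statements in 4.6 and footnote 11 that all patients are followed.

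**The concern.** Kaplan-Meier assumes that patients censored at a given time have the same subsequent risk of death as comparable patients still under observation. Here the planned censoring date is the stop date plus 24 months, and the stop date is set largely by progression, toxicity or decline. After month 24 the survivors who stopped earliest leave the risk set first, and the remaining curve rests increasingly on patients who stayed on drug longest. It would still be read as the curve for the whole arm.

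The late part of the curve may attract attention. Section 1.4.1 describes the class pattern for anti-CTLA-4 antibodies as few responses, but durable ones, with OS prolonged in a proportion of patients. The same survival times feed the exploratory Cox models in Section 10.3.

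The waiver for patients entering another study acts at any time after stopping, including before month 24, when more patients are at risk. Entry to a further trial is also unlikely to be unrelated to prognosis.

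**Working it through.** **1. Planned censoring time.** Let S be months from first dose to stopping, between 0 and about 24. Planned censoring for a survivor is C = S + 24.

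- S = 2 gives C = 26.
- S = 12 gives C = 36.
- S = 24 gives C = 48.

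The rule therefore censors no one before about month 24. At month 36 only patients treated for at least 12 months can still be at risk.

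**2. Figures in the plan.** There is no OS figure to reproduce: no median, hazard ratio, event count or landmark. The power statement in Section 10.3 concerns the primary immunologic endpoint and has no bearing here.

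**3. What sets the sign.** At time t after month 24, the patients being censored are survivors who stopped at t - 24. The curve is too high if their later hazard exceeds that of patients still at risk. It is too low if, having survived 24 months since stopping, they are at lower risk than recent progressors. If S is independent of survival there is no bias.

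**4. Size, by simulation under assumptions.** Drug stops at progression or 24 months (with toxicity stops in some runs), and censoring is at stop + 24. All survival inputs are assumptions. Except in the long-responder mixture, median time to progression was varied from 2 to 8 months and median survival after progression from 5 to 12 months. The table gives Kaplan-Meier minus true OS in percentage points.

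| Assumed model | Month 24 | Month 36 | Later |
|---|---|---|---|
| Constant hazards, median progression 2 months | 0 | about 0 | within simulation noise |
| Constant hazards, median progression 4 to 8 months | 0 | +0.2 to +0.9 | +0.1 to +1.7 (month 47) |
| Frailty in progression, or shared with survival | 0 | +0.8 to +1.7 | +1.7 to +3.1 (month 47) |
| Mixture: 10-30% long responders (median PFS 18-24 months; others 2.5-3; post-progression median 8-10) | 0 | +1.9 to +2.9 | +2.8 to +4.5 (month 42) |
| Post-progression hazard falling with time (Weibull shape 0.6), no frailty | 0 | -1.0 to -1.1 | -2.1 to -2.3 (month 47) |
| Stop time independent of survival | 0 | about 0 | within 0.1 |

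Letting treatment run past progression, as Section 6.4 permits, reduced the month-36 bias under a long-responder mixture to about +1.4. Adding frailty in progression to the falling-hazard model turned its bias from about -1.0 to +0.8 at month 36.

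**5. Bias against imprecision.** In one mixture scenario true OS at month 36 is 13.5% and the Kaplan-Meier value 15.8%, a bias of 15.8 - 13.5 = 2.3 points. With the cap of 15 patients per arm (Section 3.0), all fully followed, the standard error is sqrt(0.135 × 0.865 / 15) = 0.088, or 8.8 points. Pooling all 45 gives sqrt(0.135 × 0.865 / 45) = 0.051, or 5.1 points. The bias is 2.3 / 8.8 = 0.26 of one per-arm standard error. In that scenario 0.135 × 45 = 6.1 patients are alive at month 36, but only about 3 are still followed.

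**6. The waiver.** The documents give no rate of entry to other studies, so its effect is not quantified. None of the runs includes it. The zeros at month 24 describe the stop-date rule alone.

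**The case against.** Four points can be made for the plan.

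- **Direction.** A reader might infer that the late curve is biased upward. The documents do not establish this. They give no progression or survival figures for this population under these regimens, and step 4 shows the sign changing with the assumed model. Section 1.4.1 makes a durable-responder subgroup plausible, and so an upward error the likelier one, but that section draws mainly on melanoma.
- **Link to prognosis.** Section 6.4 allows treatment beyond confirmed progression, and Section 4.2 allows a restart when re-operation shows no significant tumor. Both loosen the tie between stop date and prognosis. They weaken it but do not remove it, since decline and toxicity still end treatment.
- **Size.** OS is secondary, arms are small, and few patients remain at risk after month 30. Imprecision outweighs the bias. This stands, although the rule adds to the imprecision by ending observation of some survivors.
- **Arm comparisons.** A reader might infer that late differences between arms would be products of the follow-up rule. The plan specifies no OS test between arms and no late landmark, and unequal follow-up does not by itself bias Kaplan-Meier. That inference is not supported.

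The reverse overstatement is also tempting: that every patient has planned follow-up to month 24, so cutting the curve there solves everything. The waiver in Section 4.6 contradicts it.

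**Conclusion.** The concern holds in a limited form. Tying the end of survival follow-up to the stop date makes independent censoring doubtful after about month 24, and the waiver for patients entering another study can make it doubtful earlier. The error from the stop-date rule is about -1 to +3 points at month 36 under the assumed inputs, probably upward if durable responders exist. Neither its sign nor its size is fixed by the documents, and sampling error there is larger. OS up to month 24, and a median reached before then, are untouched by the stop-date rule. The effect of the waiver is unknown. Because OS is a secondary endpoint, this is a minor point.

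**What to change.** **Preferred.** Amend Section 4.6 and footnote 11 of Section 5.2 so that all patients are followed for survival to one common cut-off date, or one fixed time from first dose, whenever they stopped drug. Include patients who enter another study, unless consent is withdrawn. The telephone contacts every 8 to 16 weeks already described in 4.6 can serve. The cost is a few extra survival contacts.

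**If follow-up stays as written.** State in Section 10.3 and the Study Summary that OS Kaplan-Meier estimates are interpreted only to 24 months from first dose, and report by arm how many patients were censored early on entering another study, and when. The cost is a sentence or two and loss of the curve beyond month 24. This removes the effect of the stop-date rule but only discloses the effect of the waiver.

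Neither option changes any treatment rule.
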